### ***Gut Microbiome Sample Collection and Microbial DNA Extraction:***

#### **Fecal Sample Collection, Storage, Extraction, and Sequencing (Baseline, Week 8)**

We expect to see changes in both the number and diversity of microbiota populations found in the gut as a result of treatment and reduced alcohol consumption. Because inflammation, liver function, and the gut microbiome are heavily intertwined, we will examine the relationship between changes in the gut microbiome with changes in inflammatory biomarkers in the blood (cytokines and blood monocyte cell response to LPS challenge) and liver function as a result of both RP and MBRP therapy. Fecal samples will be collected from participants using at-home kits and then stored at -80°. Microbial DNA will be extracted from fecal samples and then analyzed to determine how many and which bacterial species are present in the gut. Gut microbiome data will be collected at baseline and 8 weeks so that we can monitor changes in number and diversity of microbial DNA pre and post-intervention.

Due to the COVID-19 situation we are collecting remote data only and will return to our original protocol when it is safe to do so. The remote RESEARCH STUDY DESIGN will be as follows:

Because of the remote nature of the study, we will not be collecting the data mentioned above: MRI data, microbiome samples, or blood data.

We will be administering the parts of this study that can be done remotely through contact with a research assistant: All therapy sessions (mentioned above), and the Validating Self-report Measures listed directly below.

Additionally, due to the necessity of the remote nature attributable to COVID: All participants will need access to the internet whether by computer, smartphone, or other device such that they can complete this study. A research assistant will send unique links to participants that they will simply click on in order to participate, applications such as: Zoom (an internet application that allows us to see

and talk with the participant), Qualtrics and REDCap (online survey platforms), and DocuSign (an internet application that allows us to send forms for signatures).

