### **Baseline Session**

After arriving at the lab, qualified participants will (1) complete an informed consent form, and then (at either the same session or a separate session), participants will (2) complete a breath alcohol test, (3) complete a urine toxicology screen, (4) provide a blood sample for assays of peripheral inflammatory markers and DNA methylation, (5) fill out the baseline questionnaires, (6) and take several neurocognitive tasks. Participants will also be given a gut microbiome sample collection kit at the end of the session and will return it to their first scheduled session (7).

Subjects will be breathalyzed before every session starts, including all therapy sessions. Any subject that has a positive BAL or who reports drinking will be rescheduled for that appointment. A participant who blows a BAC over 0.00 will be given one chance to reschedule his/her appointment for the next day. If s/he comes in the next day with a breath alcohol greater than 0.00 then this session will be counted as “missed.” If a subject accumulates more than one “missed” session, they will be automatically dropped from the study on the grounds that they failed to follow explicit study directions properly. Participants will not receive compensation if a session is terminated due to failure to follow the abstinence instructions. They will be informed of this contingency during the phone screen, consent visit and is stated the consent form.

A urine toxicology screen will be administered to insure that subjects have not recently used illicit drugs including, sedatives, opiates, cocaine, or amphetamines.

A member of our research team who has completed a certified training in phlebotomy will collect the blood sample. The blood draw procedures will involve collecting venous blood (40 ml) venipuncture of a peripheral arm vein using standard, sterile phlebotomy techniques. The samples will be tested for cytokine levels and epigenetics using equipment at the CINC.

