Subjects will then complete baseline questionnaires related to their demographics, history of drinking, smoking and drug use, and alcohol craving (measures listed below). Also, subjects will take six neurocognitive tests using the NIH toolbox application, which will assess their cognitive function in terms of memory and attention. If not eligible for the MRI, subjects will be randomly assigned to receive MBRP or RP for the next 8 weeks at the end of their baseline session and will also be given their microbiome sample collection kits at the end of the session. They will return the sample kits at their next scheduled session. Subjects will be compensated \$30 for completion of the baseline appointment.

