### **End of Treatment (8 weeks)**

At the end of treatment session, subjects will continue with their usual session with a therapist (including a BAC test), and either before or after their appointment, complete a set of follow-up outcome measures including questionnaires and neurocognitive tests, and provide a blood sample. Subjects will be compensated \$30 for completion of this session, plus an additional \$15 for completing each therapy session (weeks 1-3 and 5-7), for a total of \$90 if they have attended all 6 sessions. Participants will receive their second gut microbiome sample collection kits at the end of the session and will return them using a pre-paid, pre-addressed envelope that we will provide for them.

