### Resting State Connectivity

- For this sequence, participants will be asked to just lie still and stay awake. No other actions on their behalf are needed. This resting state scan will be collected to derive measures of functional connectivity in the left and right executive control networks (LECN/RECN) following our previously published procedures (Weiland et al., 2014). These networks will be identified using functionally defined ROIs/nodes. The nodes for the LECN include:

*10 minutes*

dorsolateral prefrontal cortex (DLPFC), left middle/superior frontal gyrus (MFG), left superior parietal gyrus/angular gyrus (PAR), left inferior/middle temporal gyri (TL), right crus I/crus II/Lobule VI (CE), and left thalamus (TH). The RECN nodes include: right DLPFC, right MFG, right PAR, right medial superior frontal gyrus (mSFG), left CE, and right caudate (CU). Functional connections between nodes, each pairwise correlation defined as an edge, will be calculated and used to create a correlation matrix between the time-series of all nodes within each network for each subject. A Fisher r-to-z transformation will be applied to r-values to yield z-scores. Connectivity strength as a primary global measure of connectivity for each network will be calculated as the mean of all pairwise correlations between nodes within each network as well as other graph theory metrics (e.g., degree, efficiency, centrality). The framewise displacement (FD) for each subject will be calculated across the entire resting state run from the image motion parameter and used a covariate in the analyses.

Visit/Session	Procedures/Tools	Location	Time to Complete
Baseline Session	
 
• Informed consent; Study orientation; BAC test; Urine drug test; Questionnaires; Neurocognitive
 
	CINC	2 hours and 30 minutes

	tests; Blood draw; receive microbiome kit		
MRI Scan I	
 
• BAC test; Pregnancy test; MRI
 
	CINC	1 hour
Goal-setting Session	
 
• BAC test; a goal setting session with a therapist to discuss drinking reduction goals for the next 8 weeks; return microbiome kit
 
	CINC	1 hour

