MBRP (or RP) Therapy Sessions (weeks 1-3 and 5-7)	
 
• BAC test; Mindfulness Relapse Prevention or Relapse Prevention therapy session with a trained therapist
 
	CINC	1 hour each session (6 hours total)
Intermediate Session (week 4)	
 
• BAC test; MBRP (or RP) therapy session; Questionnaires; Blood draw
 
	CINC	2 hours
End of Treatment Session (week 8)	
 
• BAC test; MBRP (or RP) therapy session; Questionnaires; Neurocognitive tests; Blood draw; receive microbiome kit
 
	CINC	2 hours
Mail-in Sample from Home	
 
• Subject will mail-in their collection kit back to our lab in a pre-paid, pre-addressed envelope.
 
	At Home	5 minutes

Follow-up Session (week 20)	
 
• BAC test; Questionnaires; Blood draw
 
	CINC	1 hour
Follow-up Session (week 32) & MRI Scan II	
 
• BAC test; Questionnaires; Blood draw; Pregnancy test; MRI scan
 
	CINC	1 hour (2 hours with scan)
Check-In Session (week 33)	
 
• BAC test; a check-in session with a therapist to discuss potential relapse.
 
	CINC	30 minutes
TOTAL TIME		Approximately 16 hours (18 hours with MRI)	

Due to the COVID-19 situation we are collecting remote data only and will return to our original protocol when it is safe to do so. The remote PROCEDURES will be as follows:

**BASELINE SESSION:** The first study appointment is an orientation and consent session, also referred to as the Baseline session. For this appointment, the participant will meet with a research assistant who will take them through the informed consent document and give them an opportunity to ask any questions about their participation in the study. The participant will show their ID over Zoom to the confirm they are between 21-60 years old. Then a research assistant will use Docusign to electronically sign the consent form and send it to the participant to sign. Signed consent forms will be stored securely on our server in a password protected folder.

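### Stool kits are handed in at baseline but posted at week 8, so within-group microbiome change cannot be separated from a change in handling before freezing; the arm comparisons are not biased by a common shift

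*Combined protocol and SAP*

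**What the plan says.** Section XI, Baseline Session, gives participants a home kit at the end of the visit and says they "will return it to their first scheduled session". The paragraph on questionnaires and randomisation in the same section agrees: "They will return the sample kits at their next scheduled session". The visit table in section XI lists "return microbiome kit" at the Goal-setting Session, which takes place on site.

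At week 8 the route changes. Under End of Treatment (8 weeks), participants receive a second kit and "will return them using a pre-paid, pre-addressed envelope that we will provide for them". The visit table has a separate mail-in row: "Subject will mail-in their collection kit back to our lab in a pre-paid, pre-addressed envelope".

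Section IV describes handling in one sentence: "Fecal samples will be collected from participants using at-home kits and then stored at -80" degrees. It gives the purpose of the two samples as "so that we can monitor changes in number and diversity of microbial DNA pre and post-intervention", and it expects those changes to follow from both therapies.

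In the Data Analysis Plan, Exploratory Aim 1 opens with a pre-post comparison. It then specifies regressions of microbiome values on age, gender, fruit and vegetable intake and the arm contrast, before and after treatment. It also proposes to relate microbiome change to change in inflammation and liver function. None of these models has a term for handling. Hypothesis 5 concerns differences between MBRP and RP before and after treatment.

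**The concern.** Every baseline sample reaches the freezer by one route and every week-8 sample by another. If the time or conditions between collection and freezing affect which bacterial DNA is recovered, the within-group change contains that effect together with any biological change. Nothing in the planned data can divide the two.

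The quantity matters because section IV expects microbiota to change under both treatments. A between-arm contrast cancels whatever the two arms share, so only the within-group change speaks to that expectation, and that is the comparison the change of route affects. The planned links with inflammation and liver function also use microbiome change. A shift of equal size in everyone would leave such an association alone, but delays that differ between participants would add noise to the change score.

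**Working it through.** The plan gives no sample size or error rate for the microbiome aim, so there is no figure to reproduce. The check has three parts.

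**1. Can route and visit be separated?** Take a two-visit, two-arm design with columns for intercept, visit, arm, visit × arm and return route. Route is 0 (handed in) at baseline and 1 (posted) at week 8 for everyone, so its column equals the visit column. The matrix has 5 columns and rank 4. A route effect is not estimable alongside a visit effect.

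**2. How large could the effect on a pre-post comparison be?** Inputs:
- Number of pairs, n = 75. Section XIII, Microbiome and Alcohol Data Sharing, plans about 150 metagenomes; 150 / 2 = 75 if every sample is paired. The pairing is an inference.
- Within-person correlation, ρ = 0.5 (assumption).
- Handling shift, h, in SD units (assumption, starting from zero because the documents give no value).
- No true biological change.

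The SD of a paired difference is √(2(1 − ρ)) = √(2 × 0.5) = 1.0. The expected z is h × √75 / 1.0 = 8.66h. The false-positive rate of a two-sided 0.05 test is Φ(z − 1.96) + Φ(−z − 1.96).

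| Shift h (SD) | Expected z | False-positive rate |
|---|---|---|
| 0 | 0 | 5% |
| 0.1 | 0.87 | 14% |
| 0.2 | 1.73 | 41% |
| 0.3 | 2.60 | 74% |

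For h = 0.2, varying ρ from 0.3 to 0.7 moves the false-positive rate from 31% to 61%. Within a single arm (half the pairs, ρ = 0.5), h = 0.2 gives 23%. These figures describe a paired test of pooled change, which the Data Analysis Plan does not write out. They illustrate sensitivity and do not estimate an error rate of a specified analysis.

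**3. Are the arm comparisons affected?** Let the true changes be δ_M (MBRP) and δ_R (RP), and add the same shift h to both arms at week 8. The difference in change is (δ_M + h) − (δ_R + h) = δ_M − δ_R, so h cancels. It cancels in the week-8 arm contrast for the same reason. A simulation with 20,000 runs, 37 per arm, ρ = 0.5 and a common shift of 0.5 SD gave false-positive rates of 5.0% for the week-8 contrast and 4.9% for the difference in change.

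**The case against.** The best defence is that the stated hypothesis and the specified regressions are about arms. Hypothesis 5 compares MBRP with RP, and the models fit the arm contrast at each visit, where both arms share a route. This stands. A reader might infer that the change of route undermines Hypothesis 5, and the documents do not support that: both the visit-specific contrasts and the arm difference in change survive a common shift. The remaining condition is that handling does not itself differ by arm.

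A reader might also infer that posted samples wait longer than hand-delivered ones. The documents do not support this either. The baseline sample waits at home until the next session, for an unstated interval, and for scanned participants it is not clear whether that session is the MRI visit or the Goal-setting Session. The baseline delay could be shorter than, similar to or longer than the post. A difference in handling is established; its direction is not.

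Nor can it be said that times go unrecorded. The documents do not mention recording them, and kit labels or laboratory procedures may sit elsewhere. A stabilising kit could make any shift negligible, but none is named.

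Posting at week 8 is understandable, since the next visit in the table is week 20. Even with matched routes, within-group change would lack an untreated comparator, because both arms receive active treatment. Matching routes removes one competing explanation and leaves others, such as time itself.

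What survives is narrower: the plan sets out to interpret pre-post change and, as written, confounds it with handling.

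**Conclusion.** The concern holds for within-group pre-post change and for nothing wider. The procedures text and the visit table agree on the two routes, so the alignment of route with visit is the planned design. The size of any shift cannot be taken from the documents. Under the stated assumptions, a shift of 0.1 SD would do little (z = 0.87), 0.2 SD would fall short of 1.96 on average (z = 1.73), and 0.3 SD would exceed it (z = 2.60). It would be wrong to conclude that a spurious pre-post finding is expected; the point is that a pre-post finding, if seen, could not be attributed. The aim is exploratory and the remote COVID-19 version collects no stool, so this is a low-cost improvement and does not threaten the trial's main conclusions.

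**What to change.** For in-person participants:
- Use the same return route at both visits. The prepaid envelope already exists, so posting both kits is the simplest choice.
- Record collection date and time and freezer date and time on each kit. This also confirms that the baseline sample was taken before therapy began.
- Use hours to freezing as a covariate in a sensitivity analysis only, and only where the times overlap between visits. Without overlap, adjustment cannot separate delay from visit.
- For samples already collected, base conclusions on the between-arm contrasts (week 8 and difference in change), and do not attribute within-group pre-post change to treatment.

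The cost is postage for the baseline kits, two date-and-time fields, and loss of the check that the baseline kit is in hand at the Goal-setting Session. The recorded collection time covers the timing part of that check, but not non-return.

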### **Follow-up Assessment I (20 weeks)**

At this follow-up session, all subjects will take a BAC test, complete a set of self-report outcome measures and provide a blood sample. Subjects will be compensated \$50 for completing this assessment (\$30 for completing self-report measures and \$20 for providing blood samples). For subjects who are unable to come into the laboratory, the option of completing self-report measures online (via Qualtrics) will be provided for a \$30 compensation.

Participants who are unable to come into the laboratory will be sent an email, with an anonymous link to the same Qualtrics survey that would be administered at the follow-up assessments. All surveys are administered via Qualtrics and, thus, participants will already be familiar with navigating this online survey. The email will include the following instructions:

As our study staff noted, your progress since finishing treatment is extremely important for us to understand how alcohol treatments work, and why they may work better for some individuals than others. Therefore, regardless of whether you feel you have improved, declined, or had no changes since completing treatment, your responses are equally valuable. To reimburse you for your time, we will provide a \$30 gift card.

If you choose to proceed, here is the link to your survey: [INSERT LINK]

After clicking the link, please enter your study ID and treatment condition (see below). Please fill out this survey alone to ensure focus and anonymity. In addition, you may discontinue participation or refuse to answer any questions without penalty. Once you have completed the survey, study staff will be notified and you will receive your compensation within one week.

Your study ID is: [INSERT ID]

Your treatment condition is: [INSERT MBRP or RP]

### **Follow-up Assessment II (32 weeks) and MRI Scan II**

At this follow-up session, all subjects will take a BAC test, complete a set of self-report outcome measures and provide a blood sample. Subjects will be compensated \$50 for completing this

assessment (\$30 for completing self-report measures and \$20 for providing blood samples). For subjects who are unable to come into the laboratory, the option of completing self-report measures online (via Qualtrics) will be provided for a \$30 compensation. The same email will be sent for the second follow-up assessment as provided above.

All subjects who are eligible and selected to participate in the MRI scan portion of the study, will complete the second MRI scan during this appointment and receive an additional \$30 for completion of the second scan. Female participants will be asked to take a second pregnancy test free of charge and must have a negative result in order to go in the MRI. Following the MRI scan, a therapist will conduct an assessment with each participant after the cue exposure session to determine whether there is any residual craving or anxiety before leaving the session. Participants will also be provided with contact information for local AA and support groups for aftercare.

### **Check-in Session (33 weeks)**

Those subjects who participated in the MRI scan will return for a visit with a therapist one week after their second follow-up session. Before this session starts, participants will take a BAC test. During this session, the therapist will assess whether there were any adverse events, including lapses that may have resulted from the alcohol cues administered during the MR scan. Any adverse events will be addressed in the session and reported to the PI. At the end of their last session (33 weeks), participation in the study is complete.

Name of instrument/tool/procedure	Purpose (i.e. what data is being collected?)	Time to Complete
Questionnaire Measures Collected at Baseline Only		10 minutes
Demographics	

• A demographics questionnaire will be used to collect information on age, sex, marital status, SES, occupation, income, education, and race.

	
The Stages of Change Readiness and Treatment Eagerness Scale (SOCRATES)	

• SOCRATES (Miller & Tonigan, 1996) is an experimental instrument designed to assess readiness for change in alcohol abusers. The instrument yields three factorially-derived scale scores: Recognition (Re), Ambivalence (Am), and Taking Steps (Ts). It will be used to measure individual differences in motivation at baseline.

	

---

**Drinking History Questionnaire**

- Drinking history is measured with 12 items assessing lifetime drinking history such as current drinking, age of onset, and number of previous of attempts to quit/reduce drinking.

**Smoking History Questionnaire**

- Smoking History Questionnaire will be used to collect information on frequency and quantity of nicotine use and will be used to determine whether the treatment groups differ on nicotine consumption.

*30 minutes*

**Questionnaire Measures**  
**Collected at Baseline, 4, 8, 20,**  
**32 weeks**

**Timeline Follow Back (TLFB)**

- The TLFB (Sobell, Maisto, Sobell, & Cooper, 1979) is an assessment method that obtains estimates of daily alcohol, cigarette, and drug use. The TLFB has been shown to have good psychometric characteristics with a variety of drinker groups and can generate variables that provide a wide range of information about an individual's drinking (e.g., pattern, variability, and magnitude of drinking). This instrument requires subjects to recall from memory the number of drinks consumed for each day over the prior 30 days as well as their use of tobacco products and recreational drugs. Studies with alcoholics have shown this instrument to be reliable in assessing drinking frequencies and other behaviors such as arrests and hospitalizations (Sobell et al., 1979).

---

**Heavy Drinking Days (HDD); Drinks per Drinking Day (DDD); Percent Days Abstinent (PDA)**

- All three measures will be obtained at each assessment using the Timeline Follow Back (TLFB), a calendar-based assessment of daily alcohol and drug use (Sobell et al., 1979). The TLFB has been shown to have good psychometric characteristics among a variety of drinker groups and can generate variables that provide a wide range of information about an individual's drinking (e.g., pattern, variability, and magnitude of drinking). HDD is the primary behavioral outcome that will be analyzed.

